Any adverse event (AE) and/or unanticipated problem (UP) will be reported to the investigator monitor immediately by one of the investigators. Hypo- and hyperglycemia will not be considered AEs unless participant has positive ketones or displays symptoms of hypoglycemia such as: loss of consciousness, slurred speech, hospitalization or EMS services called. One of the investigators will always be on-call during the closed-loop studies and will write up a description of the adverse event/unanticipated problem. All reportable new information (RNI) will be reported to the IRB within five calendar days after the PI learns of the event. RNI is any information that might meet the regulatory definition of an unanticipated problem involving risks to participants or others or serious or continuing noncompliance that might impact the criteria for IRB approval. The report will be submitted to the IRB by the principal investigator or study coordinator. A summary of all UP's and adverse events, including those that do not meet the requirement for RNI, will be submitted with the continuing review. The FDA will be notified of any unanticipated adverse event related to the use of the study device. Notification will be made within 10 days after the Principal Investigator becomes aware of the event.

Confidentiality Procedures:

To protect confidentiality, standard institutional practices will be followed as described in the OHSU Information Security and Research Data Resource Guide

(http://ozone.ohsu.edu/cc/sec/isg/res_sec.pdf) to maintain the confidentiality and security of data collected in this study. Study staff will be trained regarding these procedures. See IRB protocol 19858 for a complete description of the confidentiality and security of the study data collected during this study to be stored in the OregonAPC repository.

[figure not shown]
Data for this project will be stored in an AWS server developed by our group that has undergone a security review.

Paper files will be stored in locked filing cabinets in restricted access offices at OHSU. After the study, source documents will be maintained at the participating clinical center (or offsite record storage facilities) 2 years after a marketing application is approved for our group's decision support device or discontinuance of pursuit of marketing approval.

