• To evaluate performance of the OHSU Robust R-AP closed-loop system versus the OHSU MPC closed-loop system in the 4 hours following the first meal period, as measured by other glycemic outcomes.

Study Hypothesis:

We propose that the use of the OHSU Robust R-AP closed-loop system as compared to the OHSU MPC closed-loop system will decrease AUC and increase the time in range as measured by sensed glucose values.

Endpoints

Primary Endpoint:

- Incremental AUC of postprandial glucose in the 4 hours following the start of first meal. AUC (mg/dL*min) will be calculated using a trapezoidal method [20], which sums all CGM values in the 4 hour period following the meal above the starting glucose.
- Percent of time with sensed glucose between 70 180 mg/dl in the 4 hours following the start of first meal.

Secondary Endpoints (all measured in the 4 hours following the start of meals):

- Percent of time with sensed glucose <70 mg/dl across the study duration
- Number of carbohydrate treatments (defined as 15 or 20 grams of carbohydrate)
- Number of provider-administered insulin injections due to hyperglycemia
- Mean sensed glucose
- Percent of time with sensed glucose <54 mg/dl
- Percent of time with sensed glucose >180 mg/dl
- Percent of time with sensed glucose >250 mg/dl
- Mean amount of insulin delivered per day (in units/kg)

Study Type

This is a single-center, crossover trial designed to compare the glucose control resulting from the use of the OHSU Robust R-AP system as compared to the OHSU MPC AP system.

Study Population

Study population will be adults with type 1 diabetes, ages 18-65 years of age. Younger participants are excluded as it is appropriate to assess safety first in the adult population. Fifteen participants will be recruited to participate in studies.

[figure not shown]
Power Analysis

This study is to obtain feasibility and assessment of variability in the primary outcomes that will inform a future larger, sufficiently powered efficacy study. A sample size of 15 is a feasible number to recruit and complete the study in timely fashion. This sample size will allow adequate estimation of the outcomes and variability of those estimates.

Protocol Summary:

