Participants will undergo two visits at OHSU that will evaluate missed meal bolus detection. Participants will arrive at approximately 7am for all visits, be monitored through the afternoon and discharged before dinner. See **Figure 1** for a diagram of the study flow. During each of these intervention visits, participants will wear an Omnipod to deliver insulin and a Dexcom G6 CGM to measure glucose. The closed loop system will receive activity data through a Polar M600 watch worn by the participant. The studies will test the ability of the system to adapt to a missed meal bolus. For one missed meal bolus study, glucose will be controlled using the Robust R-AP closed-loop mode. During the other missed meal bolus study, glucose will be controlled using the MPC closed-loop mode. For the R-AP study, participants will eat self selected meals at 10 am and 2pm. The 10am meal will be the only meal given during the MPC study. The 10am meal will be the same across both arms. A meal bolus will not be given before any meals.

Figure 1: Study Flow Design

Subject Criteria

Inclusion Criteria:

- 1. Diagnosis of type 1 diabetes mellitus for at least 1 year.
- 2. Male or female participants 18 to 65 years of age.
- 3. Current use of an insulin pump for at least 3 months with stable insulin pump settings for >2 weeks.

- 4. HbA1c $\leq 10.5\%$ at screening.
- 5. Total daily insulin requirement is less than 139 units/day.
- 6. Willingness to follow all study procedures, including attending all clinic visits.
- 7. Willingness to sign informed consent and HIPAA documents.

Exclusion Criteria:

- 1. Individual of childbearing potential who is pregnant or intending to become pregnant or breast-feeding, or is not using adequate contraceptive methods. Acceptable contraception includes birth control pill / patch / vaginal ring, Depo-Provera, Norplant, an IUD, the double barrier method (the woman uses a diaphragm and spermicide and the man uses a condom), or abstinence.
- 2. Any cardiovascular disease, defined as a clinically significant EKG abnormality at the time of screening or any history of: stroke, heart failure, myocardial infarction, angina pectoris, or coronary arterial bypass graft or angioplasty. Diagnosis of 2nd or 3rd degree heart block or any non-physiological arrhythmia judged by the investigator to be exclusionary.
- 3. Renal insufficiency (GFR < 60 ml/min, using the MDRD equation as reported by the OHSU laboratory).

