After a run-in period of 2 hours whereby the participants are using the AP algorithms, participants will eat self selected meals around 10 am. During the R-AP study only, another meal will be given four hours later around 2 pm. The self selected meals will have a minimum of 45 g of carbohydrates, and a maximum of 120 g of carbohydrates. These self selected breakfasts will be identical across both study sessions. Participants will not enter a meal bolus for the meals. CBG and blood ketone measurements will be taken every 30 min (for safety purposes only, not for input into the AP systems) until study discharge. If CBG >250mg/dL before the lunch meal, then study will be stopped early and the participant will be given the option to return on a different day for the second meal.

The study will be stopped if:

- (1) the CBG reaches > 300 mg/dL with ketones > 0.5 mM,
- (2) the CBG reaches > 300 mg/dL for over an hour (even when ketones are <0.5 mM),
- (3) the CBG reaches > 450 mg/dL,
- (4) participants exhibit nausea or vomiting or both.

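### The secondary endpoint list gives windows that conflict with each other and with the secondary objective, and outside the first-meal window only the R-AP visit includes a second meal

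*Combined protocol and SAP*

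**What the plan says.** The Secondary Objective compares the two systems "in the 4 hours following the first meal period, as measured by other glycemic outcomes". The endpoint list that follows is headed "Secondary Endpoints (all measured in the 4 hours following the start of meals", which does not limit the window to the first meal. Two of the eight items under that header state something else:

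- "Percent of time with sensed glucose <70 mg/dl across the study duration"
- "Mean amount of insulin delivered per day (in units/kg"; the closing bracket follows.

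The other six (carbohydrate treatments, provider-given insulin injections, mean glucose, and time below 54, above 180 and above 250 mg/dL) have no window except the header's.

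The two visits differ in their meals. The Protocol Summary says "The 10am meal will be the only meal given during the MPC study", and the section on 1 day Treatment Visits says "During the R-AP study only, another meal will be given four hours later around 2 pm". Self-selected meals carry 45 to 120 g of carbohydrate, and no bolus precedes them. R-AP may dose insulin once it detects the meal, subject to investigator review.

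Statistical methods does not settle the secondary windows. It restates the primary AUC for unannounced meals in the plural and gives time in range no window. It does not say how R-AP second-meal data enter a comparison with MPC.

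**The concern.** The two visits are matched by design only up to the second meal: the 10 am meal is identical across sessions, and after about 2 pm one arm eats again and the other does not. An endpoint whose window extends past 2 pm therefore compares R-AP plus an extra meal, and any insulin dosed for it, with MPC and no such meal.

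The crossover analysis cannot repair this. The model has a system effect, a random participant effect, and terms for sequence and period. The second meal occurs at the R-AP visit whatever the order, so it is aliased with the system effect and not with period or sequence.

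Hypoglycemia and insulin delivery are natural safety measures for an algorithm that adds boluses for detected meals. Time below 70 mg/dL and insulin are also the two items that carry their own windows. The study is meant to inform a larger efficacy trial, so an unclear definition could carry forward.

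**Working it through.** The plan gives no figure to reproduce on this point. The check sets the windows side by side and derives observation times from the protocol's clock times.

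**Inputs.** First meal about 10:00, both visits (Protocol Summary). Second meal about 14:00, R-AP only. Loop start about 08:00, from 10:00 less the 2 hours described by "After a run-in period of 2 hours whereby the participants are using the AP algorithms". Earliest discharge 16:00 (1 day Treatment Visits). The Protocol Summary says only that participants will "be monitored through the afternoon and discharged before dinner", so no later end time is given.

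**Hours under each reading**, for a participant who eats lunch the same day and leaves at 16:00:

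| Reading | R-AP | MPC | Ratio |
|---|---|---|---|
| First meal only | 10:00–14:00 = 4 h | 10:00–14:00 = 4 h | 4/4 = 1.0 |
| All meals, to 16:00 | 10:00–16:00 = 6 h | 10:00–14:00 = 4 h | 6/4 = 1.5 |
| Whole visit, to 16:00 | 08:00–16:00 = 8 h | 08:00–16:00 = 8 h | 8/8 = 1.0 |

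In the whole-visit row the hours are equal but their content is not: 2/8 = 25% of R-AP time follows the second meal, and none of MPC time does.

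**Counts.** Under the all-meals reading, a carbohydrate-treatment count at the same hourly rate would be 1.5 times as high on R-AP if everyone reaches lunch and leaves at 16:00. The ratio is lower if some do not reach lunch. It should not be applied to provider insulin injections, because the protocol ties these to stopping criteria rather than to a steady rate.

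**Percent-time endpoints.** Let a be the percentage of 14:00–16:00 that R-AP participants spend below 70 mg/dL with the second meal, and b what it would have been on R-AP without it. The extra meal changes the whole-visit R-AP value by (2/8)(a − b) = 0.25(a − b). The documents give neither a nor b. The meal could lower time below 70, and insulin dosed for it could raise it, so the sign is also unknown.

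**Coherence within one visit.** Suppose, for illustration, that a participant's only low is 12 minutes below 54 mg/dL after breakfast. Under the 4-hour header, time below 54 is 12/240 = 5.0%. Over an 8-hour visit, time below 70 is 12/480 = 2.5%. The subset exceeds the whole, so mixed windows are awkward even before the arms are compared.

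**Insulin.** No rule scales a part-day visit to a day. With a common 4-hour window this affects the units and not the contrast. If the visit day is meant, the R-AP figure includes any insulin dosed for the second meal.

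**The case against.** The best defense is that the objective already fixes the window and both primary endpoints specify the first meal. The plural in the header may mean no more than one 10 am meal at each of two visits. On that reading six of the eight endpoints are balanced. This stands: for those six the problem is conditional on a reading the objective argues against.

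It does not rescue the other two. The whole-study and per-day wordings conflict with the header and the objective however the plural is read. The sponsor may have chosen whole-study time below 70 mg/dL deliberately, since the phrase is attached to that item and not to time below 54. That would be a reason to report it, but it would not remove the extra meal from one arm.

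Several stronger inferences are tempting and are not supported:

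- That the plan plainly prescribes a whole-visit comparison of time below 70 mg/dL. The item sits under a header that says otherwise, so it has no single meaning as written.
- That the second meal goes without insulin. Only the pre-meal bolus is withheld; R-AP may dose after detection.
- That R-AP visits are systematically shorter. The stop for high glucose before lunch is worded for a meal only R-AP has, but the general stopping criteria are not limited to one arm, and MPC visits can also end early. The missing-data rule truncates observation time for early leavers, which partly covers unequal duration but not the meal imbalance.
- That R-AP has twice the post-meal time. This needs a full 4 hours after the 2 pm meal, to about 6 pm, an end time the documents do not give.

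The consequence is also limited: the model and tests in Statistical methods are specified for the primary outcomes, and none is specified for the secondary ones.

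**Conclusion.** The contradiction is real and the point holds as a minor one. The secondary endpoint list disagrees with itself and with the objective. Time below 70 mg/dL and insulin have no settled window, and the other six endpoints are exposed only if the plural is read to include lunch. Under any reading that runs past 2 pm, the algorithm effect is confounded with a second meal.

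The supportable sizes are 6 h against 4 h of post-meal observation, and about 25% of a whole R-AP visit following the extra meal. Both assume lunch eaten the same day and discharge at 4 pm; the 25% also assumes that the study duration starts with the loop at about 8 am. Neither is an estimate of bias, whose size and direction the documents do not allow to be calculated.

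A reader might infer that the primary comparison is compromised. It is not: the Primary Objectives and Primary Endpoint entries are limited to the first meal. The looser wording in Statistical methods needs only to be brought into line. With 15 participants and a stated feasibility purpose, the matter should be corrected but does not threaten the study.

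**What to change.** In the secondary endpoint header, replace the plural with the first meal. State there and in Statistical methods that every R-AP versus MPC comparison uses the 4 hours from the start of the 10 am meal in both arms. This includes time below 70 mg/dL, and insulin expressed as units/kg delivered in that window. Make the primary endpoints in Statistical methods match: first meal for the AUC, and the same window for time in range.

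If whole-visit time below 70 mg/dL is wanted, report it per arm as a safety summary that notes the extra R-AP meal and the hours observed. Report R-AP second-meal data descriptively.

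The cost is a change of wording. Visits, meals, data collection and sample size stay as they are, and no data are lost. The one real concession is that whole-visit time below 70 mg/dL would no longer be a between-arm comparison.

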An assessment will take place at the beginning of the participant's first closed-loop study. We will inquire whether the participant has had changes in their medications and/or medical history to confirm the participant hasn't developed any study exclusion criteria. A capillary blood glucose (CBG) will be obtained and measured by a Contour Next glucose meter. When they arrive, participants will be given 15-20 grams of oral carbohydrate if the CBG reading is less than 70 mg/dl. CBG values > 300 mg/dl will be managed at the discretion of the investigator with a correction bolus and serum ketones will be checked. If serum ketones are ≥ 0.6 mM, the study will not be started and insulin therapy will be guided by the onsite investigator.

During each visit, glucose will be controlled using either: 1) the OHSU Robust R-AP closed-loop mode or 2) the OHSU MPC closed-loop mode. The order of the visits will be randomized. A code team is available by page at all times in all locations.

An Omnipod will be filled with Novolog or Humalog insulin for all studies. The Omnipod will be primed and inserted into the skin of the participant's abdomen or flank as directed by the manufacturer. Participants will disconnect his/her own pump and remove his/her own insulin infusion set once insulin delivery has started via the Omnipod. Participants will wear a Polar watch to inform the controller. The research staff will initialize the system and begin the closed-loop study. Two staff will review each of the settings to confirm the settings are inputted correctly. A member of the study staff will remain with the participant for the duration of the study with the study investigator on call. Research staff will set up and run the system and respond to all alerts.

The algorithm will push data up to a cloud server that can be monitored remotely every 5 minutes. The iPancreas will generate alerts on the smartphone according to Appendix D. In order to push alerts to study coordinators and study investigators, the cloud server used for remote monitoring will have a drop down menu for study staff to sign in and out for the duration of their monitoring shift. Each study coordinator and investigator listed in the menu will have a cell phone number on file that can receive texts with pushed alerts.

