Participants can be discharged after 4pm when: (1) CBG >80 and < 250 mg/dl, (2) ketones \leq 0.2 mM and (3) the participant is feeling well. For values outside this range, treatment will be at the discretion of the study investigator. Participants will be given a snack to take with them for the trip home. Participants will also be advised to monitor their glucose for any symptoms of hyperglycemia or hypoglycemia, before their next meal, and at bedtime.

Discharge from clinic

The study will be terminated and the participant's own insulin pump will be restarted. The study investigator will consult with the participant regarding appropriate insulin dosing for the remainder of the day. The Polar watch, Omnipods and Dexcom sensor will be removed from the participant. All infusion sites and the sensor site will be inspected for signs of irritation or infection. In addition, the sensor will be inspected for the possibility of breakage or fracture. If there is any evidence of sensor breakage, it will be recorded. If an area of inflammation of 1 cm or greater exists around the point of insertion, a de-identified photograph will be taken of the area and the participant will return 1-3 days later for a follow-up visit.

If a study visit is stopped prematurely, such as due to technical problems, the participant will be asked if they can repeat the study visit that was terminated early with additional compensation provided. Repeating the study visit will be optional.

Hypoglycemia Treatment Guidelines

• CBG < 70 mg/dl

Give 15 grams of oral carbohydrate.

Repeat treatment every 15 minutes as needed to raise blood glucose ≥70 mg/dl.

• Presence of STUPOR, LOSS OF CONSCIOUSNESS, or SEIZURE

Give 1 mg glucagon IM

Verify that insulin is turned off.

Further management per study investigator.

Cleaning and Disinfecting

All devices will be cleaned and disinfected between participants. The smart phone, Dexcom G6 transmitter and Omnipod PDMs are cleaned by study staff. Technicians who are disinfecting units will wash hands thoroughly and wear gloves. All items will undergo intermediate-level disinfection using Oxivir TB disposable wipes. The disinfectant will be applied and allowed to air dry. After disinfection, when the units are completely dry, they will be placed in a sealed bag labeled with participant information.

Stopping Rules

Individual study stopping rules

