Appendix C: Alert Manager Specifications

#	NAME: Activation criteria	Clearing Criteria	Algorithm specifics	Notificati on to participa nt	Re- fire Time (min)	Refrac tory Period (min)	Coordin ator push	Investi gator push	Waiti ng perio d
4	cbg_equal_or_under_4 0: CBG ≤ 40 mg/dl AND alert 4 not active	User enters CBG > 40 mg/dL after 15 minutes. Once rescue carb are entered, the waiting period starts. If CBG ≥70 at any time, alert clears.	None	"Blood glucose is below 40 mg/dl. Please take 30 gm of rescue carbohyd rates and recheck your blood glucose level in 15 minutes."	5	-	Immediately	Immediately	Waiti ng perio d ends whe n alert 13 is servi ced OR clear crite ria is met
5	cbg_under_70: CBG < 70 mg/dl AND alert 5 not active AND alert 4 not active	CBG entry ≥70 clears alert. Once rescue carbs are entered, the waiting period starts. Alert clears if activation of alert 4 is met	None	"Blood glucose is below 70 mg/dl. Please take 15 gm of rescue carbohyd	15	-	After 1st re- fire	After 2nd re- fire	Waiti ng perio d ends whe n alert 13 is servi

				rates and recheck your blood glucose level in 15 minutes.					ced OR clear crite ria is met
6	sensor_glucose_low: Sensor glucose < LOW_THRESH AND alert 4 AND alert 5 AND alert 6 not active or refractory & no CBG within last 15 minutes	CBG check OR sensor ≥ LOW_THRESH OR extreme_low_sen sor_glucose is active.	For MPC, LOW_THRESH = 70 mg/dL	"Sensor glucose is below LOW_TH RESH mg/dl. Please perform a blood glucose check now."	15	60	After 1st re- fire	After 2nd re- fire	-
7	cbg_equal_or_over_30 0: CBG ≥ 300 mg/dl AND alert 27 not active or refractory AND alert 7 not active or refractory	Ketone check	None	"Blood glucose is above 300 mg/dl. Please check the insulin pod for leaking or detachm ent and check ketone	30	120	After 1st re- fire	After 2nd re- fire	-

				levels now."					
8	sensor_glucose_high: Sensor glucose ≥ 300 mg/dl for 30 minutes within the last 45 minute period AND alert 8 AND alert 7 AND alert 27 not active or refractory AND no CBG in last 30 minutes	CBG check. OR sensor < 300	None	"Sensor glucose is over 300 mg/dl. Please perform a blood glucose check now."	30	60	After 1st re- fire	After 2nd re- fire	-
1 0	Insulin_meal_bolus_fail ure: If 50% of meal bolus is still not delivered after 20 minutes.	Auto clears	None	Insulin bolus failed to deliver, please contact the study investiga tor.	-	-	Immedi ately	Immedi ately	-

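### At CBG 40 mg/dl or below the protocol names two rescue amounts, 15 g and 30 g, and the carbohydrate-treatment endpoint does not say how a 30 g rescue is counted

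*Combined protocol and SAP*

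**What the plan says.** **Endpoint.** The Endpoints section lists, as a secondary endpoint, "Number of carbohydrate treatments (defined as 15 or 20 grams of carbohydrate". The header of that list sets the window: "Secondary Endpoints (all measured in the 4 hours following the start of meals". No further counting rule is given, there or under Statistical methods.

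**Treatment text.** Under 1 day Treatment Visits, a participant whose blood glucose is under 70 mg/dl, or who has symptoms, is to take 15 g. The Hypoglycemia Treatment Guidelines say the same for CBG under 70 mg/dl, "Give 15 grams of oral carbohydrate", repeated every 15 minutes as needed until glucose is at least 70. Their only other tier is for stupor, loss of consciousness or seizure. There is no separate tier at 40 mg/dl or below.

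**Alert table.** Appendix C is tiered. Alert 4 fires on "CBG ≤ 40 mg/dl AND alert 4 not active" and its message reads "Please take 30 gm of rescue" carbohydrate. Alert 5 fires on "CBG < 70 mg/dl AND alert 5 not active AND alert 4 not active" and asks for 15 g. The treatment-visit section has research staff respond to all alerts.

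**Stopping rule.** Under Individual study stopping rules, closed loop is stopped and open-loop control resumed if CBG falls below 40 mg/dl.

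**The concern.** A CBG of 40 mg/dl or below is also below 70, so staff facing that reading have two written instructions with different amounts and no statement of which one governs. That is a contradiction on a safety action, whatever the analysis.

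The same gap reaches the endpoint. Its definition names 15 g and 20 g. A rescue given exactly as alert 4 instructs is 30 g, which is neither. The analyst must then decide whether it is no treatment, one treatment or two. The trial compares a system that doses for a detected meal with one that lacks that feature, so the number of hypoglycemia treatments per arm is a comparison readers will look at. The protocol describes no blinding, so a counting rule settled after the visits could be settled with the arm known.

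**Working it through.** The plan states no figure for this point. The check sets the instructions side by side and then counts one event by hand under each reading.

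**Step 1. Amount instructed, by situation**

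| Situation | 1 day Treatment Visits | Hypoglycemia Treatment Guidelines | Appendix C |
|---|---|---|---|
| CBG 41–69 mg/dl | 15 g | 15 g | 15 g (alert 5) |
| CBG 40 mg/dl or below | 15 g | 15 g | 30 g (alert 4) |

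The texts agree in the first row and differ in the second.

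**Step 2. Amounts the endpoint recognises.** The endpoint lists 15 g and 20 g. The amounts instructed during the meal window are 15 g and 30 g. The 20 g figure appears only as the upper end of the arrival instruction, at about 7 am, before the meal at about 10 am. The definition therefore includes an amount not instructed in its window and omits one that is.

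**Step 3. Score for one event in the window**

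| Event | Literal (15 or 20 g only) | Per administration | Per 15 g unit |
|---|---|---|---|
| CBG ≤40, one 30 g rescue (alert 4) | 0 | 1 | 30/15 = 2 |
| CBG ≤40, 30 g, then one 15 g repeat | 0 + 1 = 1 | 1 + 1 = 2 | 2 + 1 = 3 |
| CBG ≤40, k doses of 15 g (Guidelines), k ≥ 1 | k | k | k |
| CBG 41–69, one 15 g rescue | 1 | 1 | 1 |

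On the literal reading, a deeper episode corrected by one 30 g rescue scores 0 while a milder one scores 1. Under the Guidelines the deeper episode scores at least 1, because treatment is repeated until glucose reaches 70 mg/dl.

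**Step 4. Overlap with the stopping rule.** Alert 4 covers CBG ≤40; the stop covers CBG <40. Only a reading of exactly 40 triggers alert 4 without the stop. The missing-data paragraph under Statistical methods truncates observation time when a participant leaves early. Neither it nor the endpoint says whether a rescue given at the moment of the stop is inside the counted window.

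**The case against.** The strongest reply is that the practical reach is small. Most of it stands.

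- **A zero score needs a narrow case.** It requires the literal reading and a single 30 g rescue that brings CBG from 40 or below to at least 70 with no repeat. If CBG recovers only to 41–69, alert 4 can clear and alert 5 then asks for 15 g, which counts. The definition can also be read as the size of one unit, making 30 g two treatments. This stands: zero is a possibility, not the expected result.
- **The episodes are visible elsewhere.** A CBG below 40 stops closed loop. Percent of time below 70 and below 54 mg/dl does not depend on grams. Hypoglycemia with signs such as loss of consciousness or slurred speech is an adverse event, and a visit stopped for severe hypoglycemia halts the whole study. This stands, so a reader should not infer that the trial would lose sight of its worst hypoglycemia.
- **Alert 4 may seldom appear.** It depends on a CBG being entered, while the half-hourly CBGs are described as safety measurements not fed to the AP systems. The table also contains an overnight refractory rule that cannot apply to a day visit, which suggests a general device specification. This lowers the likely frequency, but staff are still told to act on all alerts, and alert 4 presupposes that CBG values are entered.
- **The arrival amount.** A reader might count "participants will be given 15-20 grams of oral carbohydrate if the CBG reading is less than 70 mg/dl" as a further contradiction. It applies on arrival, before closed loop starts and outside the meal window, and it is compatible with 15 g. It plausibly explains where the 20 g in the endpoint came from.

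None of this says which amount governs at 40 mg/dl or below, or how a 30 g rescue is counted.

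**Conclusion.** The contradiction is real: 15 g and 30 g are both instructed for the same CBG, with no order of precedence. The endpoint leaves a single 30 g rescue at 0, 1 or 2, and leaves open whether a rescue at a stopped visit counts.

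The consequence is limited to one secondary count and one operational inconsistency. The primary endpoint definitions are unaffected. That such episodes should be rare is a judgement, resting on 15 participants with two staffed day visits each (30 visits if all complete); the documents give no expected rate.

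A reader might go further and infer that one or two such episodes could decide the comparison between systems. The documents do not support that. They give no event rate, they specify a test only for the primary endpoints, and they describe a feasibility study in which no decision rests on this count.

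This is a minor point, worth correcting because the correction is cheap.

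**What to change.** 1. **Endpoint.** Define the count as every rescue-carbohydrate administration in the window, whatever the grams, including one given when a visit is stopped. Total grams by arm may be reported alongside; that is optional.
2. **Instructions.** Reconcile the treatment-visit text and the Hypoglycemia Treatment Guidelines with alert 4 in Appendix C, so that one instruction applies at each CBG level. Which amount applies is for the clinical team to decide; this review takes no view.

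The cost is one endpoint sentence and one reconciliation of existing text. No new data item is needed if each rescue is recorded with its time and amount. The counting rule should be fixed before the data are examined by arm.
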